13.3.2 Definition of success and power of success

Responses to alternative therapies in this population of patients with advanced MCC resistant to PD1-axis blockade are rare, and we therefore will use a 5% response rate as the fixed benchmark upon which we hope to improve with the proposed treatment. If the true response rate with TCR-transduced cells is 25%, 16 patients yield 84% power to detect a statistically significantly improved response rate (one-sided .05) over the fixed rate of 5%. Three or more responses among 16 pts would occur with probability .04 if the true response rate is 5%, so if three or more patients respond (an observed response rate of at least 19%), we will conclude that this regimen is potentially efficacious and worthy of further

study. If power is instead assessed among the anticipated 12 patients who will receive a checkpoint inhibitor, the statistical power is reduced to 78%.

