11.6 Response Assessment

Participants will have evaluation of tumor burden at baseline (physical exam with tumor measurements, cross-sectional imaging as detailed above, RECIST and imRECIST reads of cross-sectional imaging), at 4 and 12 weeks after first T cell infusion, at 4 and 12 weeks after second infusion (if given), and then at discretion of treating oncologist (suggested frequency every 3-6 months). Patients with progressive disease on 4 week imaging but clinical stability may remain on study given the possibility of delayed clinical responses to immunotherapy. Imaging should also be performed if suspicion of progression. Imaging will be performed on a clinical basis with RECIST/imRECIST reads on a research basis. For skin/cutaneous tumors, representative/target tumors should (optionally) be photographed at key response assessment/measurement time points (day 14, 12 weeks, months 3, 6, 9, and 12 post infusion). Patients without measurable lesions will not be evaluable for response, but will be evaluable for safety endpoints.

Participants will have clinical pathology evaluation of tumor at baseline, at approximately 12 weeks after first T cell infusion, and if clinically suspected to have progression. Additional research biopsies are planned prior to T cell infusion, at 2 weeks post T cell infusion and at 12 weeks after second T cell infusion, and additional research tissue may be requested from clinical biopsies.

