13. STATISTICAL CONSIDERATIONS

13.1 Sample size and Power

Our study is a phase I/II, non-blinded interventional trial. Our target sample size is up to 16 patients (8 per year/2 years). This target is chosen for three reasons: it is achievable from an enrollment standpoint (our clinic sees between 15-20 potentially eligible patients per year), it is logistically possible from a funding and cell processing facility standpoint, and it allows >80% power to observe a statistically significant (at one-sided 0.05 level) efficacy signal that is clinically meaningful. (see below for details). With the eligibility expansion, we expect roughly 12 patients will receive a PD1 checkpoint inhibitor. For some analyses, all 16 patients will be analyzed, yet some analyses will be restricted to patients who receive a PD1 checkpoint inhibitor. See below for the impact of this on statistical power.

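### The stated power of 84% with 16 patients and 78% with 12 is not what the three-response rule delivers: exact values are 80% and 61%

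*Combined protocol and SAP*

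**What the plan says.** Section 13.3.2 sets out the efficacy test. The null is a fixed rate: "we therefore will use a 5% response rate as the fixed benchmark". The level is "one-sided .05) over the fixed rate of 5" percent. The power claim reads "If the true response rate with TCR-transduced cells is 25%, 16 patients yield 84% power". The regimen is judged worth further study if three or more patients respond, and the null probability of that result is given: "Three or more responses among 16 pts would occur with probability .04 if the true response rate is 5" percent. Section 3.1.2 repeats the requirement of at least 3 responses in 16.

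Section 13.1 gives power as one of three reasons for choosing 16 patients, because "it allows >80% power to observe a statistically significant" efficacy signal. It then says that about 12 patients are expected to receive a checkpoint inhibitor after the eligibility expansion, that some analyses will be restricted to them, and that the effect on power is described later. The only such description is in Section 13.3.2: "If power is instead assessed among the anticipated 12 patients who will receive a checkpoint inhibitor, the statistical power is reduced to 78" percent. No response cut-off is given for 12 patients.

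Section 11.6 states: "Patients without measurable lesions will not be evaluable for response, but will be evaluable for safety endpoints". Section 13.3.1 likewise limits the endpoint to patients with at least one measurable lesion. The inclusion criteria in Section 5.2 do not require measurable disease.

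**The concern.** The type I error of .04 in Section 13.3.2 is the exact binomial tail of the three-response rule, so the power of that rule should come from the same distribution. The printed 84% and 78% looked too high for it. They resemble a large-sample normal approximation, which cannot be trusted when the expected number of responses under the null is 0.8 (16 × 0.05) or 0.6 (12 × 0.05).

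Two things are at stake. A committee reading 84% and 78% would think the eligibility expansion costs the checkpoint-inhibitor analysis 6 points of power and leaves a 22% chance of missing a true 25% response rate. And the claim of more than 80% power, used to justify 16 patients, might hold only if every patient counts toward the response endpoint.

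**Working it through.** **Inputs.** From Section 13.3.2: null rate p0 = 0.05, alternative p1 = 0.25, one-sided level 0.05, success at X ≥ 3, n = 16, and n = 12 for the checkpoint-inhibitor subset.

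**Step 1: the printed figures.** The uncorrected one-sample normal approximation is

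Power = Φ{ [√n (p1 − p0) − 1.645 √(p0(1 − p0))] / √(p1(1 − p1)) }, with √(0.05 × 0.95) = 0.2179 and √(0.25 × 0.75) = 0.4330.

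- n = 16: (4 × 0.20 − 0.3585) / 0.4330 = 1.020, power 0.846 (printed 84%).
- n = 12: (3.464 × 0.20 − 0.3585) / 0.4330 = 0.772, power 0.780 (printed 78%).

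This is the only one of the methods tried that comes close to both figures. Others give, for n = 16 and n = 12: continuity-corrected 0.768 and 0.670; two-sided normal 0.805 and 0.730; arcsine 0.770 and 0.663.

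**Step 2: exact properties of the rule.** P(X ≥ 3) = 1 − P(0) − P(1) − P(2), binomial.

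- n = 16, rate 5%: 1 − 0.4401 − 0.3706 − 0.1463 = 0.0429. This reproduces the plan's .04.
- n = 16, rate 25%: 1 − 0.0100 − 0.0535 − 0.1336 = **0.803**.
- n = 12, rate 5%: 1 − 0.5404 − 0.3413 − 0.0988 = 0.0196.
- n = 12, rate 25%: 1 − 0.0317 − 0.1267 − 0.2323 = **0.609**.

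**Step 3: can any cut-off at n = 12 give 78%?**

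| Cut-off | Type I error at 5% | Power at 25% |
|---|---|---|
| ≥ 2 of 12 | 0.118 | 0.842 |
| ≥ 3 of 12 | 0.020 | 0.609 |
| ≥ 4 of 12 | 0.002 | 0.351 |

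None does. Three is the smallest cut-off that keeps the level at or below 0.05. With the three-response rule, 78% power at n = 12 needs a true rate of about 31.4%, and 84% at n = 16 needs about 26.6%.

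**Step 4: fewer evaluable patients.** Three is the smallest valid cut-off for every n from 8 to 16: two of 8 already has type I error 0.057, and three of 17 has 0.0503. The documents give no expected number of non-evaluable patients, so the range is shown.

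| Evaluable n | Type I error, ≥ 3 | Power at 25%, ≥ 3 |
|---|---|---|
| 16 | 0.043 | 80.3% |
| 15 | 0.036 | 76.4% |
| 14 | 0.030 | 71.9% |
| 13 | 0.025 | 66.7% |
| 12 | 0.020 | 60.9% |

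**Step 5: the synopsis.** It attaches power of 0.84 to a true rate of 20%, where Section 13.3.2 uses 25%. At 20% the exact power of at least 3 of 16 is 64.8%, and the normal approximation gives 72.7%.

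**The case against.** The strongest reply is that little depends on the error. With 16 patients the decision rule, its type I error, the benchmark and the sample size are all right, and 80.3% still satisfies the claim of more than 80% in Section 13.1. That stands: the 3.7-point gap at 16 would be minor on its own.

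For 12 patients, one can say that the plan states no cut-off, that the figure is introduced conditionally, and that the declared success criterion rests on 16. It is true that 3 of 12 is inferred. But the stated level leads to it, and no other cut-off gives 78% either. The 12-patient analysis is not the primary conclusion, yet 78% is the plan's only answer to a question that Section 13.1 itself raises.

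The loss of evaluable patients is disclosed in Sections 11.6 and 13.3.1, and the values for 13 to 15 patients are sensitivity figures, not demonstrated errors. That is fair. They show how little margin the 16-patient claim has.

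Finally, the documents name no method for the power figures, and the normal approximation gives 84.6% for 16 patients, which would round to 85% and not 84%. So it is a likely source of the figures, not an established one. The conclusion does not depend on it.

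**Conclusion.** The concern holds. At a true response rate of 25%, the three-response rule has 80.3% power with 16 patients, not 84%, and 60.9% with 12, not 78%. The second figure is the material one: it is 17 points too high and cannot be obtained from any exact one-sided .05 test with 12 patients. The chance of missing a true 25% rate in the checkpoint-inhibitor subset is 39%, not 22%. Going from 16 to 12 patients costs about 19 points (80.3 − 60.9), not the 6 implied (84 − 78).

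The claim of more than 80% power holds by 0.3 of a point, and only if all 16 places are filled and every patient is evaluable for response. These results rest on the plan's own 5% and 25% rates, independent patients with a common response rate, and, for 12 patients, the cut-off of 3 that the .05 level requires.

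**What to change.** In Section 13.3.2, replace the two power figures with exact values: 80% for at least 3 of 16 (type I error .043) and 61% for at least 3 of 12 (type I error .020), both at a true rate of 25%. State that 3 responses is the cut-off for any evaluable number from 8 to 16, and give exact power for 12 to 16 evaluable patients as tabulated above. Writing down the 12-patient cut-off also rules out a later choice of 2 of 12, with its 11.8% type I error.

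In Section 13.1, say that power is about 80% only if all 16 patients are evaluable for response. In the synopsis, align the assumed true rate and power with Section 13.3.2; if 20% is retained there, exact power is 65%.

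The cost is protocol wording and less favourable stated figures. The 3-of-16 rule does not change and no extra patients are needed.

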13.4 Secondary and Exploratory analyses

Progression-free and overall survival will be estimated using the method of Kaplan and Meier, with time zero the time of first T cell infusion. Given the small size of the trial, many of the secondary and exploratory endpoints are descriptive or hypothesis generating in nature and are thus underpowered for formal statistical analysis. Standard methods will be used to estimate each of the secondary endpoints.

14. DATA AND SAFETY MONITORING PLAN

14.1 Overall Scope of Monitoring Activities

Institutional support of trial monitoring will be in accordance with the Fred Hutch /University of Washington Cancer Consortium Institutional Data and Safety Monitoring Plan (DSMP). Under the provisions of this plan, Fred Hutch Clinical Research Support coordinates data and compliance monitoring conducted by consultants, contract research organizations, or Fred Hutch employees unaffiliated with the conduct of the study. Independent monitoring visits occur at specified intervals determined by the assessed risk level of the study and the findings of previous visits per the institutional DSMP.

In addition, protocols are reviewed at least annually and as needed by the Consortium Data and Safety Monitoring Committee (DSMC), Fred Hutch Scientific Review Committee (SRC) and the Fred Hutch /University of Washington Cancer Consortium Institutional Review Board (IRB). The review committees evaluate accrual, adverse events, stopping rules, and adherence to the applicable data and safety monitoring plan for studies actively enrolling or treating patients. The IRB reviews the study progress and safety information to assess continued acceptability of the risk-benefit ratio for human patients. Approval of committees as applicable is necessary to continue the study.

The trial will comply with the standard guidelines set forth by these regulatory committees and other institutional, state and federal guidelines. The conduct of this trial will be further monitored by an independent Data and Safety Monitoring Board (DSMB) in accordance with an approved DSMB Charter.

14.2 Monitoring the Progress of Trial and Safety of Participants

The first level of trial oversight for this protocol will be provided by the Principal Investigator, the Research Nurse, and the Research Coordinator(s), who will provide continuous oversight of the trial. These individuals will meet at least monthly to review recently acquired data, stopping rules, and adverse events. Serious adverse events will be reviewed upon occurrence to ensure prompt and accurate reporting to the IND Sponsor, appropriate committees, and regulatory agencies as described above. The data recorded in the research charts and protocol database will be compared with the actual data available from the medical record and/or clinical histories. Data detailed in the research case report forms (CRFs) will include the nature and severity of all grade 3-5 adverse events. The Principal Investigator and all other investigators on the protocol have received formal training in the ethical conduct of human research.

The IND Sponsor will ensure routine trial monitoring as described above and will review Serious Adverse Events and other reports of safety issues promptly upon receipt from the PI.

A DSMB will be in place and will meet after three patients have received treatment (or sooner if requested) to review the data as it relates to AEs and determine whether trial may proceed to part II dose level. The purpose of the DSMB meetings is to review the conduct of the trial to date and assess safety and toxicity of the study intervention. The DSMB will review all grade 3 or greater CTCAE v5.0 toxicities and SAEs and determine whether the study should be prematurely discontinued due to excessive toxicity consistent with **Section 13**. Ad hoc meetings may be scheduled as needed.

15. DATA MANAGEMENT/CONFIDENTIALITY

The medical record containing information regarding treatment of the patient will be maintained as a confidential document, within the guidelines of the Fred Hutch and the University of Washington Medical Center.

The investigator will ensure that data collected conform to all established guidelines for coding collection, key entry, and verification. Each patient is assigned a unique patient number to assure patient confidentiality. Information forwarded to the FDA, NIH, NCI or other agencies about patients on this protocol refers to patients by a coded identifier and not by name. Patients will not be referred to by this number, by name, or by any other individual identifier in any publication or external presentation. The licensed medical records department, affiliated with the institution where the patient receives medical care, maintains all original inpatient and outpatient chart documents. Additional clinical data may be made available from the Fred Hutch core database which is managed and verified independent of the research group.

The research team will maintain Case Report Forms (CRFs) and associated research documentation for each patient treated under the protocol. This documentation includes both clinical data and study-specific documents for each patient. The Principal Investigator or a designee will verify completed CRFs against source documentation on an ongoing basis as they are completed for individual patients. Data required for analysis of patients treated on this protocol will be maintained in a password-protected study-specific database. Data from the CRFs are keyed directly into the database by authorized research staff and verified on an ongoing basis.

16. TERMINATION OF STUDY

The study will terminate after the last treated patient has completed 15 years of follow-up as described in this protocol.

The PI or IND Sponsor may terminate the study at any time. The IRB and FDA also have the authority to terminate the study should it be deemed necessary.

APPENDIX A: Schedule of Evaluations

9845: ATTAC-MCC

Assessments	Screening Evaluation (Fred Hutch/local)		Fred Hutch Post T-cell Infusion #1 Evaluations		(Fred Hutch/local-may combine w/ Avelumab eval bloodwork)		Fred Hutch Post T-cell Infusion #2 Evaluations		(Fred Hutch/local-may combine w/ Avelumab eval bloodwork)		Fred Hutch/Local Avelumab infusion days ⁱ		Short-term Follow-Up ^c					
	Pre-treatment Evaluation ^a		T-cell Infusion #1 (Day 0)		Day +1	Day +3	Day +7	Day +10	Day +14 (Avelumab - dose 1)	Day +21	Day +28	Day +56	Day +28	Day +56				
review of any tumor lesion																		
HLA typing	X																	
Imaging and Tumor Measurements^f																		
CT C/A/P or PET-CT		X									X ^j		X	X	X	X ^j	X	X
CT affected area (if not covered w/ above)		X									X	X				X	X	X
MRI Brain		X									X	X				X	X	X
Measurement and photo of palpable tumors		X					X				X	X				X	X	X
Interventions																		
Clinical Biopsy (to pathology) ^g		X									X	X				X	X	X
Research Biopsy (may be combined w/ clinical; to [name] Lab D3-235) ^g		X		X _k			X				X	X		X ^k		X	X	X

9845: ATTAC-MCC

Assessments	Screening Evaluation (Fred Hutch/local)										Fred Hutch Post T-cell Infusion #1 Evaluations										Fred Hutch Post T-cell Infusion #2 Evaluations																
	Pre-treatment Evaluation ^a					T-cell Infusion #1 (Day 0)					Fred Hutch/Local Avelumab infusion days ⁱ					(Fred Hutch/local-may combine w/ Avelumab eval bloodwork)					Fred Hutch Post T-cell Infusion #2 Evaluations					(Fred Hutch/local-may combine w/ Avelumab eval bloodwork)		Fred Hutch/Local Avelumab infusion days ⁱ		Short-term Follow-Up ^c							
Leukapheresis	X																																				
Interferon Gamma ^h	X																																				
T-cell Infusion	X																																				
Avelumab ⁱ									X		X										X		X				X										
Clinical Blood Work / Safety Laboratory Evaluations																																					
CBC w/ diff, platelet count	X				X	X	X	X	X	X	X	X				X	X	X	X	X	X	X	X	X	X	X	X	X									
Comprehensive Metabolic Panel	X				X	X	X	X	X	X	X	X				X	X	X	X	X	X	X	X	X	X	X	X	X									
LDH	X				X	X	X	X	X	X	X	X				X	X	X	X	X	X	X	X	X	X	X	X	X									
12-Week Restaging ^c																																					
Pre-treatment Evaluation ^a										T-Cell Infusion #2 (Day 0) ^d					Fred Hutch Post T-cell Infusion #2 Evaluations					(Fred Hutch/local-may combine w/ Avelumab eval bloodwork)		Fred Hutch/Local Avelumab infusion days ⁱ		Short-term Follow-Up ^c													
Leukapheresis					Day +1		Day +3		Day +7		Day +10		Day +14		Day +21		Day +28		Day +56		Day +28		Day +56		X												
Interferon Gamma ^h					X										X		X																				
T-cell Infusion					X										X																						
Avelumab ⁱ																					X																
12-Week Restaging ^c																																					
Pre-treatment Evaluation ^a										Leukapheresis (if indicated)					Interferon Gamma					Pre-treatment Biopsy		12-Week Restaging ^c		Short-term Follow-Up ^c													
Leukapheresis					X										X		X																				
Interferon Gamma ^h					X										X		X																				
T-cell Infusion					X										X		X																				
Avelumab ⁱ															X		X																				
Month 6, 9, and 12 post T-cell Infusion 1#1																																					

9845: ATTAC-MCC

Research Blood Work (all to Research Cell Bank)

60 mL lavender top	X				X	X			X						X	X								X
20 mL serum sep	X						X			X						X								X
40 mL lavender top					X	X	X			X	X				X	X	X			X	X			

9845: ATTAC-MCC

NOTE: The proposed days of all treatments and assessments are approximate and may vary due to scheduling, clinical, or other factors

^a Tests obtained as part of routine clinical care may be substituted, and may be omitted for Cycle 2 evaluation as long as within protocol-specified window

b Medical history should initially include a full history of all findings at diagnosis, time of enrollment, prior history, and response to therapy, as well as relevant other medical issues, family and social history, medications, allergies. Subsequent medical histories may be focused as appropriate

^c For all other medical issues, family and social history, medications, allergies. Subsequent medical history may be reviewed as appropriate. 12-week evaluation strongly preferred to be at Fred Hutch and 6, 9, and 12-month evaluations preferred at Fred Hutch. However, if patient cannot travel, these evaluations may be performed locally

d Please see section 6.4 for details on determination of one versus two cycles of T cell therapy, and guidance for timing of second T-cell administration

^e Please see inclusion criteria for further details on determination of tumor virus status

Diagnostic imaging evaluations preferred to be at Fred Hutch but may be performed elsewhere if travel or insurance issues preclude Fred Hutch scans.

Baseline imaging must be obtained within 45 days prior to start of first planned FH-MCVA2TCR infusion.

Biopsies may be omitted or retimed at discretion of PI based on clinical appropriateness

^h Administered 3 times weekly through d28

ⁱ Please see section 6.5 for additional details and suggested guidance on standard of care avelumab or pembrolizumab. If patients receive pembrolizumab, certain evaluations may be rescheduled to match the pembrolizumab schedule (e.g., the D28 evaluations may be performed at D35, and the D84 evaluations may be performed at D77).

CT chest/abdomen/pelvis (CAP) + involved areas w/ IV contrast mandatory, PET CT optional per clinical status

^k Biopsy after 2-4 doses of IFN- β , day of or day before cell infusion

APPENDIX B: Research Sample Checklist

Please note that many of the listed research studies are optional pending clinical course, and may be replaced by newer or alternate assays that answer the same general question. Note that the selected studies will be batched, and results are not anticipated to be available in “real-time”. Leftover materials from all time points may be archived.

RECIPIENT RESEARCH EVALUATIONS BEFORE T CELL INFUSION

SAMPLE	TIME	TEST	TUBE	VOL. (Approx.)	LAB
Blood	At Enrollment	T cell persistence and functional studies, epitope spreading, scRNAseq, clonality, RCL baseline	Lavender top	60 mL	RCB
Blood	At Enrollment	Cytokine levels and MCPyV antibody levels (research)	Serum separator	20 ml	RCB
Tumor	At Enrollment	Single cell RNA sequencing	RPMI	4 cores or equiv	ICTPL
Tumor	At Enrollment	T cell localization and tumor microenvironment characteristics	Formalin	2 core or equiv; in addition to clinical core	[name] D3-235
Tumor	At Enrollment	Archive	RPMI	Any addtl tissue	[name] D3-235
Tumor	Pre-Treatment	Single cell RNA sequencing	RPMI	4 cores or equiv	ICTPL
Tumor	Pre-Treatment	T cell localization and tumor microenvironment characteristics	Formalin	2 core or equiv; in addition to clinical core	[name] D3-235
Tumor	Pre-Treatment	Archive	RPMI	Any addtl tissue	[name] D3-235
Blood	Day 0	Cytokine levels (research)	Serum separator	10 ml	RCB
Blood	Day 0	T cell baseline persistance, function	Lavender top	40 ml	RCB

RECIPIENT RESEARCH EVALUATIONS AFTER T CELL INFUSION

SAMPLE	TIME	TEST	TUBE	VOL. (Approx)	LAB
Blood	Day 1	Cytokine levels (research)	Serum separator	10 ml	RCB
Blood	Day 1	T cell persistence, phenotype	Lavender top	40 ml	RCB
Blood	Day 3	Cytokine levels (research)	Serum separator	10 ml	RCB
Blood	Day 3	T cell persistence and functional studies	Lavender top	40 ml	RCB
Blood	Day 7	Cytokine levels (research)	Serum separator	10 ml	RCB
Blood	Day 7	T cell persistence and functional studies	Lavender top	60 ml	RCB
Blood	Day 14	Cytokine levels (research)	Serum separator	20 ml	RCB
Blood	Day 14	T cell persistence and functional studies, epitope spreading, scRNAseq, clonality	Lavender top	60 ml	RCB
Blood	Day 21	Cytokine levels (research)	Serum separator	10 ml	RCB
Blood	Day 21	T cell persistence	Lavender top	20 ml	RCB
Blood	Day 28	Cytokine levels (research)	Serum separator	10 ml	RCB
Blood	Day 28	T cell persistence, immunophenotype	Lavender top	40 ml	RCB
Blood	Day 56	Cytokine levels (research)	Serum separator	10 ml	RCB
Blood	Day 56	T cell persistence, immunophenotype	Lavender top	40 ml	RCB
Blood	Day 84	T cell persistence, epitope spreading, scRNAseq, immunophenotype, clonality, RCL	Lavender top	60 ml	RCB
Blood	Day 84	Cytokines, research serologies	Serum separator	20 ml	RCB
If second infusion, please refer to study schedule					
Blood	Day 180	T cell persistence, epitope spreading, immunophenotype, clonality, RCL	Lavender top	60 ml	RCB
Blood	Day 180	Cytokines, research serologies	Serum separator	20 ml	RCB

Blood	Day 270	T cell persistence, epitope spreading, immunophenotype, clonality, RCL	Lavender top	60 ml	RCB
Blood	Day 270	Cytokines, research serologies	Serum separator	20 ml	RCB
Blood	Day 365	T cell persistence, epitope spreading, immunophenotype, clonality, RCL	Lavender top	60 ml	RCB
Blood	Day 365	Cytokines, research serologies	Serum separator	20 ml	RCB
Blood	Annual years 2-15	T cell persistence, RCL	Lavender top	20 ml	RCB
Blood	Annual years 2-15	serologies	Serum separator	10 ml	RCB
<hr/>					
Blood	Clinical events	T cell persistence, epitope spreading, immunophenotype, clonality, RCL, scRNAseq (all optional/TBD)	Lavender top	Up to 60 ml	Discuss with study staff
Blood	Clinical events	Cytokine levels	Serum separator	20 mL	Discuss with study staff
<hr/>					
Tumor	Day + 14	Single cell RNA sequencing	RPMI	4 cores or equiv	[name] D3-235
Tumor	Day + 14	T cell localization and tumor microenvironment characteristics	Formalin	2 cores or equiv	[name] D3-235
Tumor	Day +14	Archive	RPMI	Any addtl tissue	[name] D3-235
Tumor	Day + 84	Single cell RNA sequencing	RPMI	4 cores or equiv	[name] D3-235
Tumor	Day + 84	T cell localization and tumor microenvironment characteristics	Formalin	2 cores or equiv; in addition to clinical core(s)	[name] D3-235
Tumor	Day + 84	Archive	RPMI	Any addtl tissue	[name] D3-235
Tumor	Clinical event	Single cell RNA sequencing	RPMI	4 cores or equiv	[name] D3-235

Tumor	Clinical event	T cell localization and tumor microenvironment characteristics	Formalin	2 cores or equiv; in addition to clinical core	[name] D3-235
--------------	----------------	--	----------	--	----------------

